2.3 Patient disposition, demographics, disease history and medical history

The Full Analysis Set (FAS) will be used for all baseline and demographic summaries and listings unless otherwise specified. No inferential statistics will be provided.

Basic demographic and background data

All demographic and baseline disease characteristics data will be summarized and listed. Categorical data, e.g. gender, age groups: <65 and \geq 65 years, race, ECOG performance status, FGFR status (FGFR1/2/3 Amplified/Mutated/Translocated), will be summarized by frequency counts and percentages; the number and percentage of patients with missing data will be provided. Continuous data, e.g. age, weight, height, body mass index, will be summarized by descriptive statistics (N, mean, median, standard deviation, minimum and maximum). BMI (kg/m²) will be calculated as weight[kg] / (height[m]²) using weight at Baseline.

Diagnosis and extent of cancer (disease history)

Diagnosis and extent of cancer will be tabulated for primary site of cancer, details of tumor histology/cytology and histological grade.

Medical history

Medical history and ongoing conditions, including cancer-related conditions and symptoms entered on (e)CRF will be summarized and listed. Separate summaries will be presented for ongoing and historical medical conditions. The summaries will be presented by primary system organ class (SOC) and preferred term (PT). Medical history and current medical conditions will be coded using the Medical Dictionary for Regulatory Activities (MedDRA) terminology. The MedDRA version 20.1 used for reporting will be specified in the CSR and as a footnote in the applicable tables/listings.

2.3.1 Patient disposition

The following patient disposition information will be summarized for patients in the FAS:

- Enrolled patients who remained on treatment or discontinued treatment, based on the end of treatment (e)CRF (note that patients remained on treatment if the last known date the patient took study drug is later than the cut-off date)
- Primary reasons for end of treatment (EOT).
- Number (%) of patients who are discontinued and have entered the 30 day safety follow-up (based on the 'End of Treatment Phase Completion' page);
- Number (%) of patients who have entered the survival follow-up (based on the 'End of Treatment Phase Completion' page).
- Primary reasons for end of study

A listing of EOT details will be produced. Patients enrolled but not treated will be listed along with the reason for discontinuing from the study. Additionally, a listing of screen failure

patients, with reason for screen failure will be produced. Since screening failures are not part of any analysis sets, they will not be included in any of the summary tables.

Protocol deviations

The number (%) of patients in the FAS with any protocol deviation will be tabulated by deviation category (as specified in the study Data Handling Plan). Protocol deviations leading to exclusion from analysis sets will be tabulated separately. All protocol deviations will be listed.

Analysis sets

The number (%) of patients in each analysis set (defined in Section 2.2) will be summarized.

2.4 Treatments (study treatment, rescue medication, concomitant therapies, compliance)

2.4.1 Study treatment / compliance

Duration of exposure, actual dose intensity (ADI) and relative dose intensity (RDI) will be summarized. The number (%) of subjects who have dose reductions or interruptions, and the reasons, will be summarized.

Subject level listings of all doses administered on treatment along with dose change reasons will be produced.

The safety set will be used for all summaries and listings of study treatment.

Duration of exposure to study treatment

The duration of exposure is calculated as detailed below.

For patients who discontinued permanently from the study as of the data cut-off date:

$$\text{Duration of exposure (days)} = (\text{end date of study drug} + X) - (\text{start date of study drug}) + 1,$$

where study drug is BGJ398 and X is the number of days from last administered dose to the next planned dose taking into account the minimal allowed dosing interval. If the last dose of a cycle was taken later than the scheduled cycle length (28 days), X will be set to 0 days. For BGJ398, X equals to 0 if the cycle day of the last dose is less than 21 days; otherwise, X equals to (28 – cycle day of the last dose).

For patients who are still on-treatment as of data cut-off date:

$$\text{Duration of exposure (days)} = \text{data cut-off date} - (\text{start date of study drug}) + 1.$$

Summary of duration of exposure of study treatment in weeks will include categorical summaries and continuous summaries (i.e. mean, standard deviation etc.). Duration of exposure will be categorized into time intervals (i.e. < 4 weeks, 4 - < 8 weeks, 8 - < 12 weeks, 12 - < 16 weeks, 16 - < 24 weeks, 24 - < 32 weeks and >= 32 weeks); frequency counts and percentages will be presented for the number (%) of subjects in each interval.

Exposure will be summarized on the Safety Set.

Cumulative dose

Cumulative dose of a study treatment is defined as the total dose given during the study treatment exposure and will be summarized for each of the study treatment components.

The **planned cumulative dose** for a study treatment component refers to the total planned dose as per the protocol up to the last date of investigational drug administration.

The planned cumulative dose is not summarized/listed. It is used for relative dose intensity calculations.

The **actual cumulative dose** refers to the total actual dose administered, over the duration for which the subject is on the study treatment as documented in the DAR (e)CRF.

For patients who did not take any drug the cumulative dose is by definition equal to zero.

Relative dose intensity

Actual dose intensity (ADI) for patients with non-zero duration of exposure is defined as follows:

$$\text{ADI (mg / day)} = \text{Actual Cumulative dose (mg)} / \text{Duration of exposure to study treatment (day)}.$$

For patients who did not take any drug the ADI is by definition equal to zero.

Planned dose intensity (PDI) is defined as follows:

$$\text{PDI (mg / day)} = \text{Planned Cumulative dose (mg)} / \text{Duration of exposure (day)}.$$

Relative dose intensity (RDI) is defined as follows:

$$\text{RDI} = \text{ADI (mg / day)} / \text{PDI (mg / day)}.$$

Dose reductions, interruptions or permanent discontinuations

The number of subjects who have dose reductions, dose interruptions, or dose permanent discontinuations, and the reasons, will be summarized. 'Dose Changed', 'Dose interrupted', and 'Dose permanently discontinued' fields from the DAR (e)CRF will be used to determine the dose reductions, dose interruptions, and permanent discontinuations, respectively. **Note:** planned 1 week off in dosing schedule will not be collected or counted as dose interruption. The corresponding field 'Reason' for dose changed, dose interrupted, and dose permanently discontinued will be used to summarize the reasons.

A dose reduction is defined as a decrease in total daily dose from the protocol planned dose, and a decrease from the previous non-zero dose, even if this decrease has been directly preceded by an interruption, and the dose change flag is checked. For example, in the sequence 125 mg – 0 mg – 100 mg, the 100 mg dose will be counted as a reduction.

A dose interruption is defined as an instance that no study drug (0 mg) is taken when the protocol planned dose is non-zero. For example, in the sequence 125 mg – 0 mg – 100 mg, the 0 mg dose will be counted as an interruption.

2.4.2 Prior, concomitant and post therapies

Prior anti-cancer therapy

The number and percentage of patients who received any prior anti-neoplastic medications, prior anti-neoplastic radiotherapy or prior anti-neoplastic surgery will be summarized. For prior medications. Summaries will include prior antineoplastic regimens, total number of regimens, setting at last treatment based on end date, best response at last treatment based on end date. For prior radiotherapy, locations and setting at last radiotherapy will be summarized. For prior surgery, procedure at last surgery (biopsy or other) and residual disease will be summarized.

Separate listings will be produced for prior anti-neoplastic medications, radiotherapy, and surgery.

The above analyses will be performed using the FAS.

Concomitant medications

Concomitant therapy is defined as all interventions (therapeutic treatments and procedures) other than the study treatment administered to a patient coinciding with the study treatment period. Concomitant therapy includes medications (other than study drugs) starting on or after the start date of study treatment or medications starting prior to the start date of study treatment and continuing after the start date of study treatment.

Concomitant medications will be coded using the World Health Organization (WHO) Drug Reference Listing (DRL) dictionary that employs the WHO Anatomical Therapeutic Chemical (ATC) classification system and summarized by lowest ATC class and preferred term using frequency counts and percentages. Surgical and medical procedures will be coded using MedDRA and summarized by SOC and preferred term. These summaries will include:

1. Medications starting on or after the start of study treatment but no later than 30 days after start of last dose of study treatment and
2. Medications starting prior to start of study treatment and continuing after the start of study treatment.

All concomitant therapies will be listed. Any concomitant therapies starting and ending prior to the start of study treatment or starting more than 30 days after the last date of study treatment will be flagged in the listing. The safety set will be used for all concomitant medication tables and listings.

2.5 Analysis of the primary objective

The primary objective of the study is to assess the anti-tumor activity of BGJ398 for patients with GBM and/or other glioma subtypes with FGFR1-TACC1, FGFR3-TACC3 fusion and/or activating mutation in FGFR1, 2 or 3.

2.5.1 Primary endpoint

PFS rate at 6 months (PFS6) as defined by RANO criteria assessed by the investigator will be the primary endpoint.

[figure not shown]
Non Surgery Group: PFS is defined as the number of days from the first day of treatment to the date of the first documented disease progression or date of death, whichever occurs first.

Surgery Group: PFS is defined as the number of days from the first day of treatment after surgery to the date of the first documented disease progression or date of death, whichever occurs first.

2.5.2 Statistical hypothesis, model, and method of analysis

A Bayesian design will be used in order to estimate the PFS6 rate and to provide inferential statements based on the uncertainty of this quantity. Progression free survival will be modeled using a Weibull distribution. The Weibull distribution is a flexible distribution which allows for time varying hazard rate. The probability density function is given by $f(x) = \nu\lambda x^{\nu-1}\exp(-\lambda x^\nu)$ where ν is a shape parameter and λ a scale parameter. Prior distributions will be placed on both parameters to carry out the analysis. For the scale parameter, a normal (mean = 0, standard deviation = 2.236) distribution will be used on the log of the parameter. For the shape parameter, an exponential with rate 1 will be used. These priors correspond to a prior probability of unacceptable efficacy (PFS6 <16%) of 65 %, and clinically relevant efficacy (PFS6 > 40%) of 25% (see Figure 2-1 below).

Figure 2-1 PFS6 prior distribution

The posterior distributions will be updated with all the data available at the time of the analyses from the patients in the PPS who are evaluable for the primary analysis. Once updated, the posterior probability that the true PFS6 rate at the dose of BGJ398 used in the study lies in the following categories will be summarized:

- [0, 16%) unacceptable efficacy
- [16%, 25%) limited efficacy
- [25%, 40%) moderate efficacy
- [40%, 100%] clinically relevant efficacy

Data from both the treatment groups will be pooled together for this analysis, since we expect to observe similar 6-month PFS rates for these two groups. The study will be considered a success at the final analysis if

- there is at least 50% confidence that BGJ398 has clinically relevant efficacy (that is, $\text{Post Prob}(\text{PFS}_{6\geq 40\%}) > 50\%$), and
- there is at least 80% confidence that BGJ398 has either moderate efficacy or clinically relevant efficacy ($\text{Post Prob}(\text{PFS}_{6\geq 25\%}) > 80\%$).

2.5.3 Handling of missing values/censoring/discontinuations

Patients who discontinue the study and are lost to follow-up without a known date of progression or death due to any cause on or before the cut-off date will be censored in the primary analysis at the date of their last available tumor assessment.

2.5.4 Supportive analyses

As a supportive analysis, Kaplan-Meier estimates of the PFS rate at 4, 6, 12, 16, 18 and 24 months, 25th/75th percentile and median PFS will be derived together with 95% confidence intervals. PFS will also be presented descriptively using Kaplan Meier plots. This analysis will be done with all patients in both the treatment groups pooled together.

2.6 Analysis of the key secondary objective

Not applicable.

2.7 Analysis of secondary efficacy objective(s)

The secondary objectives of the study is to assess the anti-tumor activity of BGJ398 based on objective response rate and overall survival using RANO criteria.

Each patient will be evaluated for all potential sites of tumor lesions at Screening and every 8 weeks after starting study treatment until disease progression.

On-study tumor assessments have a ± 7 day window, except for the first post-baseline tumor assessment and for confirmatory scans (4 weeks +7 day window only). The first post-baseline tumor assessment should be performed on day 1 of cycle 3 (+7 day window permitted) after starting treatment. There will be a tumor assessment at the End of Treatment (+ 7 days) if the patient discontinues for any reason other than disease progression and the last tumor assessment has been performed > 28 days prior to this day.

2.7.1 Objective Response Rate

Objective response rate (ORR) is defined as the proportion of patients with a best overall response of Complete Response (CR) or Partial Response (PR), as per the RANO criteria.

The ORR analysis will include patients from the FAS who have measurable disease (as per RANO) at their baseline scan. ORR will be reported with 95% confidence interval and response will be listed.

This analysis will be done for all patients in the PPS as well as the FAS in both treatment groups pooled together.

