10.1.2 Safety Set

The Safety Set includes all patients who received at least one dose of BGJ398 and have at least one valid post-baseline safety assessment. Patients with FGFR1, 2, 3 and 4 amplifications enrolled prior to protocol amendment 2 will be included in the safety set. These patients will be included in the FAS and their data will be listed and summarized as described below, however they will not be part of the per-protocol set which will be used for the primary analysis.

The statement that a patient had no AE (on the AE eCRF) constitutes a valid safety assessment.

Patients will be classified according to treatment received, where treatment received is defined as:

- The treatment assigned if it was received at least once, or
- The first treatment received when starting therapy with study treatment if the assigned treatment was never received.

[figure not shown]

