1.1 Study design

The study is planned to enroll patients with recurrent GBM in two groups. Non Surgery Group enrolls patients who are not candidates for surgery. Patients in Non Surgery Group receive BGJ398 on a three weeks on, one week off schedule. Surgery Group enrolls patients who are surgical candidates. Patients in Surgery Group receive BGJ398 for 5-10 days prior to surgery. After recovery of surgery (a minimum of two weeks and no more than six weeks following surgery), patients in Surgery Group receive BGJ398 on a three weeks on, one week off schedule. Patients from both Non Surgery Group and Surgery Group are evaluated for tumor response and progression by Gd-enhanced MRI every 8 weeks until disease progression/discontinuation from study using RANO criteria.

The study plans to enroll 34 adult patients with histologically confirmed recurrent GBM and/or other glioma subtypes with FGFR1-TACC1, FGFR3-TACC3 fusion and/or activating mutation in FGFR1, 2, or 3.

Figure 1-1 Study design

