1.2 Study objectives and endpoints

Objectives and related endpoints are described in Table 1-1 below.

Table 1-1 Objectives and related endpoints

Objective	Endpoint
Primary	
To assess the anti-tumor activity of BGJ398 for patients with GBM and/or other glioma subtypes with FGFR1-TACC1, FGFR3-TACC3 fusion and/or activating mutation in FGFR1,2 or 3, based on PFS6	PFS rate at 6 months as defined by RANO criteria as assessed by the investigator
Secondary	
To further assess the anti-tumor activity of BGJ398 for patients with GBM and/or other glioma subtypes with FGFR1-TACC1, FGFR3-TACC3 fusion and/or activating mutation in FGFR1,2or 3, based on ORR	ORR (patients with measurable disease) as defined by RANO criteria as assessed by the investigator

Objective	Endpoint
To further assess the anti-tumor activity of BGJ398 for patients with GBM and/or other glioma subtypes with FGFR1-TACC1, FGFR3-TACC3 fusion and/or activating mutation with in FGFR1,2or 3, based on OS	Overall survival (OS)
To characterize the safety and tolerability of BGJ398	Safety: type, frequency, and severity of AEs and SAEs; Tolerability: dose interruptions, reductions and dose intensity, and evaluations of laboratory values

2 Statistical methods

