2.2 Analysis sets

Treatment group will be named as: Non Surg BGJ398 125 mg and Surg BGJ398 125 mg. If there are no patients in the surgery group, only Non Surg BGJ398 125 mg will be presented.

Full Analysis Set

The Full Analysis Set (FAS) includes all patients who received at least one dose of BGJ398. The FAS will be used for all listings of raw data. Unless otherwise specified the FAS will be the default analysis set used for all analyses.

Per protocol set (PPS)

The Per-Protocol Set (PPS) will consist of a subset of patients in the FAS (with FGFR1-TACC1, FGFR3-TACC3 and/or activating mutations in FGFR1, 2 or 3) who are compliant with requirements of the CSP. The PPS will include patients who have an adequate tumor assessment at baseline, a follow-up tumor assessment >8 weeks after starting treatment unless disease progression is observed before that time, and no protocol deviations.

[figure not shown]
Safety

The Safety Set includes all patients who received at least one dose of BGJ398 and have at least one valid post-baseline safety assessment.

The statement that a patient had no AE (on the AE (e)CRF) constitutes a valid safety assessment.

The treatment received is defined as:

- The treatment assigned if it was received at least once, or
- The first treatment received when starting therapy with study treatment if the assigned treatment was never received.

Patient Classification:

Patients may be excluded from the analysis populations defined above based on the protocol deviations entered in the database and/or on specific subject classification rules defined in Table 2-3.

Table 2-3 Determination of analysis set membership

Description used to report Protocol Deviations	Protocol deviation IDs	Analysis set(s) to be excluded
Inclusion criteria not met	INC01, INC02, INC04	PPS
Use of prohibited concomitant medication	WITH04, WITH05, TRT05	PPS

Withdrawal of Informed Consent

Any data collected in the clinical database after a subject withdraws informed consent from all further participation in the trial, will not be included in the analysis. The date on which a patient withdraws full consent is recorded in the (e)CRF.

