2.7.2 Overall Survival

Non-Surgery Group: overall survival (OS) is defined as the time from the date of start of treatment to the date of death due to any cause or the date of last contact (censored observation) at the date of data cutoff.

Surgery Group: OS is defined as the number of days from the first day of treatment after surgery to the date of death due to any cause or the date of last contact (censored observation) at the date of data cutoff. If the patient does not receive at least one post-surgical dose of BGJ398 (i.e., C1D1), the patient will be excluded from the overall survival analysis.

The survival time for patients without documentation of death prior to analysis data cutoff, will be censored at the last date the patient was known to be alive prior to the cutoff date. Survival time for patients with no post-baseline survival information will be censored on the date of start of treatment.

OS will be analyzed using the Kaplan-Meier method. Survival rate at 4, 6, 8, 12, 18 and 24 months and median OS will be estimated along with 95% confidence intervals.

This analysis will be done for all patients in the PPS as well as the FAS in both treatment groups pooled together.

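### ORR and OS are planned only in the FAS and the PPS, and neither is the set of all treated patients with an FGFR fusion or activating mutation that the secondary objectives name

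*SAP*

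**What the plan says.** **Objectives.** SAP Table 1-1 limits the ORR objective to "glioma subtypes with FGFR1-TACC1, FGFR3-TACC3 fusion and/or activating mutation in FGFR1,2or 3, based on ORR". The OS objective has the same limit, ending "activating mutation with in FGFR1,2or 3, based on OS". Protocol Table 3-1 agrees.

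**FAS.** SAP 2.2: "The Full Analysis Set (FAS) includes all patients who received at least one dose of BGJ398". It has no molecular condition and is the default set. Protocol 10.1.2 says of amplified patients enrolled before Amendment 2: "These patients will be included in the FAS". The same section keeps them out of the PPS. The SAP does not repeat this. SAP 1.1 says "The study plans to enroll 34 adult patients with histologically confirmed recurrent GBM and/or other glioma subtypes" and describes all of them as fusion or mutation patients, yet SAP 2.3 lists amplified as a category of baseline FGFR status.

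**PPS.** Protocol 10.1.3 and SAP 2.2 restrict it to fusion or mutation patients. Both also require an adequate baseline scan and a follow-up scan more than 8 weeks after starting treatment, unless progression comes earlier. The protocol excludes patients with major deviations. The SAP text excludes patients with any deviation, although its Table 2-3 lists only specific deviation codes.

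**Analyses.** For ORR: "The ORR analysis will include patients from the FAS who have measurable disease (as per RANO) at their baseline scan". For OS: "This analysis will be done for all patients in the PPS as well as the FAS in both treatment groups pooled together". The ORR section closes with the same sentence. Neither document plans ORR or OS by alteration type, or says which of the two sets gives the main secondary result.

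**The concern.** An objective should have at least one analysis in its own population. Here one set is too wide and the other too narrow.

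- **FAS.** Amplified patients are no longer eligible under Amendment 2, whose rationale is that amplification is a poor stand-in for a fusion. If they respond less or die sooner, they dilute both estimates.
- **PPS.** A treated fusion or mutation patient can be removed by what happens after the first dose. For ORR such a patient is a non-responder, and removal raises the rate. For OS, protocol 7.1.5 follows all enrolled patients for survival, so removal discards collected data and conditions survival on later events.

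A reader would have two figures per endpoint and no statement of which one answers the objective.

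**Working it through.** **1. The plan's own figures.** The documents give no power or precision for ORR or OS. The planned sizes are PPS 24 and FAS 34 (protocol 10.4.1), so 34 − 24 = 10 patients lie outside the PPS. The one result tied to a PPS of 24 is the 86.1% probability of success at a true PFS6 of 50% (protocol 10.8). Simulating 1,000 trials with the stated Weibull priors, one patient per month, exponential event times and an interim on the first 10 patients gave 85.4%. This supports 24 as the PPS size behind the design. It says nothing about ORR or OS.

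**2. Who is in each set.**

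| Patient | Objective | FAS | PPS |
|---|---|---|---|
| Fusion/mutation, qualifying scans, no excluding deviation | yes | yes | yes |
| Fusion/mutation, progression before 8 weeks, other conditions met | yes | yes | yes |
| Fusion/mutation, no progression and no scan beyond 8 weeks, or no adequate baseline scan, or excluding deviation | yes | yes | no |
| Amplified, enrolled before Amendment 2 | no | yes | no |

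The last two rows make up the 10. How they divide is not stated.

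**3. ORR.** Let *k* be the target patients outside the PPS, so that 10 − *k* are amplified. Assume 5 responders, all in the PPS, and measurable disease in everyone. Then FAS ORR = 5/34, target ORR = 5/(24 + *k*) and PPS ORR = 5/24.

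**4. OS.** Assume exponential survival with medians of 9 months (target) and 6 months (amplified). Twelve-month survival is 0.5^(12/9) = 39.7% and 0.5^(12/6) = 25.0%. FAS survival = [(24 + *k*) × 0.397 + (10 − *k*) × 0.250]/34. For *k* = 3 this is (27 × 0.397 + 7 × 0.250)/34 = 36.7%.

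| Amplified | Target outside PPS | ORR, FAS | ORR, target | ORR, PPS | 12-month OS, FAS | 12-month OS, target |
|---|---|---|---|---|---|---|
| 10 | 0 | 14.7% | 5/24 = 20.8% | 20.8% | 35.4% | 39.7% |
| 7 | 3 | 14.7% | 5/27 = 18.5% | 20.8% | 36.7% | 39.7% |
| 4 | 6 | 14.7% | 5/30 = 16.7% | 20.8% | 38.0% | 39.7% |
| 0 | 10 | 14.7% | 5/34 = 14.7% | 20.8% | 39.7% | 39.7% |

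In the 7/3 split the target ORR is 3.8 points above the FAS and 2.3 points below the PPS. The FAS understates 12-month OS by 3.0 points.

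**5. Sensitivity to the zero-response assumption.** With a target ORR of 33% and 5 amplified patients, FAS ORR is (29 × 0.33 + 5 × 0)/34 = 28.1%. If amplified patients respond at 5%, it is (29 × 0.33 + 5 × 0.05)/34 = 28.9%. The dilution vanishes if both groups respond alike.

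**6. The scan rule against the schedule.** The first post-baseline scan is on cycle 3 day 1, target day 57 (SAP 2.7 and Table 2-1). Since 57 − 1 = 56 = 8 × 7, an on-time scan falls at exactly 8 weeks. Read strictly, the more-than-8-weeks rule could remove a progression-free patient whose only scan was on time.

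**The case against.** **The mixture is disclosed, and the protocol prefers the PPS.** This is true. Protocol 10.1.2 says where amplified patients go, protocol 10.4.1 puts the efficacy focus on the PPS, and SAP 2.3 tabulates FGFR status. A reader might infer that the plan hides the mixture; the documents do not support that. However, the focus statement sits under the primary variable, the SAP does not carry it to ORR or OS, and the PPS is not the objectives' population either.

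**The PPS loses fewer patients than it seems.** A reader might infer that everyone who stops early, for example for toxicity, is dropped. Protocol 7.1.4 and 7.1.5 say otherwise. Patients who stop treatment for reasons other than progression stay on study, with MRI every 8 weeks until progression, new anticancer therapy or death. Early progressors stay in the PPS. The RANO appendix (14.3.2) also counts failure to return because of death or deterioration as progression, which may keep some early deaths. On the scan rule, the loss is mainly patients who withdraw, are lost to follow-up or start other therapy before a qualifying scan.

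**The consequences are limited.** ORR and OS carry no hypothesis, key-secondary status or power claim, and responses are listed, so ORR could be partly rebuilt by hand. The exact 95% interval for 5/27 is 6.3% to 38.1%, much wider than the gaps above. All of this stands and bounds the importance of the point. It does not supply the missing estimate, and no comparable OS estimate can be read from a planned table.

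**Conclusion.** The point holds as a mismatch between objectives and analysis sets. Followed as written, the plan yields no ORR or OS estimate in all treated fusion or mutation patients, except at the two extremes. If all 10 patients outside the PPS are amplified, the PPS is the target population; if none is, the FAS is.

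In the 7/3 illustration the ORR figures differ by 2 to 4 points on either side of the target value, and 12-month OS by 3 points in the FAS. These sizes rest on assumed responder counts, no response in amplified patients, universal measurability and assumed OS medians. Only the set sizes of 34 and 24 come from the documents.

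A reader might infer that the FAS and PPS figures always bracket the target value. Under the stated assumptions that is shown for ORR only. The direction of any PPS bias for OS is uncertain, because patients removed could live longer or shorter than those kept. Nor do the documents say that 10 amplified patients were enrolled; 10 is the most that the planned sizes allow.

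This should be changed, but it concerns secondary estimates and does not affect the primary success rule.

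**What to change.** - **SAP 2.2:** define a molecularly eligible FAS: all treated patients with a documented FGFR1-TACC1 or FGFR3-TACC3 fusion and/or activating FGFR1, 2 or 3 mutation. State there, as the protocol does, that the full FAS also holds amplified patients, and align SAP 1.1 with this.
- **SAP 2.7.1:** make this the main set for ORR, among patients with measurable disease at baseline, counting non-evaluable patients as non-responders. This fits protocol 14.3.1.2, which asks for measurable disease and at least one dose.
- **SAP 2.7.2:** make it the main set for OS, keeping the stated exclusion of surgical patients with no post-surgical dose.
- Keep the PPS and full FAS as supportive, show amplified patients separately, and apply the same flag to the supportive PFS analysis in SAP 2.5.4.
- Reconcile the PPS deviation wording between the protocol, SAP 2.2 and SAP Table 2-3, and state whether an on-time cycle 3 day 1 scan meets the 8-week rule.

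Cost: one flag built from FGFR status, which is already a baseline variable, and reruns of existing tables. No new data are needed.
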